#### Intercurrent events:

- Treatment failure, defined as meeting any of the criteria outlined in Section 2.2.5 (eg, use of prohibited medications, use of rescue therapy or alternative treatments, or discontinuation of zetomipzomib or placebo)
- Increased dose for background medications and/or corticosteroids
- Change in background medications

Note: Study discontinuation, loss to follow-up, and other missing data are not intercurrent events and are not reflected in estimands, but instead represent limitations to the data to be addressed in the analysis via missing data handling.

Table 6: Estimand for Comparative Analysis between Zetomipzomib and Placebo

Attribute	Primary Estimand	Secondary Estimand(s)/ Sensitivity Analysis
Population of interest	ITT for randomized patients with Class III/IV+/- V LN	ITT for randomized patients with Class III/IV+/- V LN and pure Class V (sensitivity analysis)  PP population for randomized patients with Class III/IV+/- V LN
Endpoints of interest	CRR at Week 37	Same as primary estimand
Population-level summary	Difference in proportion of patients in CRR at Week 37 between zetomipzomib and pooled placebo	Same as primary estimand
Intercurrent events a	
 
Use Composite method
 
Treatment failure         (non-responder)
 
Discontinuation of         zetomipzomib or placebo         (non-responder)b
 
Use of rescue therapy or         alternative treatments (non-responder)
 
Use of prohibited medications         (non-responder)
 
Increased dose for background         medications and/or         corticosteroids         (non-responder)
 
Change in background         medications (non-responder,         unless permitted per         Sections 6.2.1 and 6.2.2 where         observed efficacy data will be         used for analysis)
 
	
 
(1) Use Treatment Policy method
 
For patients who had an IE and remained in the study, the observed efficacy data at Week 37 will be included in the analysis of CRR at Week 37, respectively
 
(2) Use Principal stratum
 
For patients in the strata of the ITT population who do not require additional medication (including rescue therapy and protocol prohibited medications) and change in background medications
 
For patients who reach EOT
 

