Missing data	NRI will be applied to the primary estimand for missing data at Week 37 (ie, early discontinuation of study, lost to follow-up, or due to other intercurrent events)	Other missing data handling methods (such as tipping point analysis, MI for binary endpoints [ie, CRR, PRR], and MI for continuous endpoints [ie, percentage change from Baseline in UPCR]) may be applied.

<sup>a Prior to the Week 37 visit.

In the primary analysis of the primary estimand, the proportion of patients achieving CRR at Week 37 for the treatment comparison between zetomipzomib and placebo (separately for each of the 2 dose groups and pooled placebo) will be carried out in the ITT using CMH test at 2-sided 5% level of significance, stratified by the randomization stratification factors (3 factors

b Exception: For patients who discontinue zetomipzomib or placebo without using any rescue therapy or protocol prohibited medications and remain in the study, their observed efficacy data will be included in the analysis. CRR=complete renal response; EOT=end of treatment; ITT=intent-to-treat population; LN=lupus nephritis; MI=multiple imputation; NRI=non-responder imputation; PP=per-protocol; PRR=partial renal response; UPCR=urine protein to creatinine ratio.

for this study; see Section 3.2.1). Results will be expressed as the number of patients achieving CRR, CRR proportion, weighted difference in CRR proportions, odds ratio, associated 2-sided 95% CI, and p-value (for each pairwise comparison between zetomipzomib and placebo). A bar graph showing the proportion of patients achieving CRR by treatment group with the weighted treatment difference and CMH p-value will be produced. For patients whose CRR at Week 37 cannot be adequately determined (including missing data, early study discontinuation, or lost to follow-up), their CRR will be imputed using an NRI approach. For patients meeting the treatment failure criteria prior to the Week 37 visits, their CRR after discontinuation and at the Week 37 visit, respectively, will be imputed using NRI.

The primary analysis of the primary estimand and secondary estimand(s) will be carried out for randomized patients (ITT) with Class III/IV+/- V LN (N=249).

A sensitivity analysis for each estimand (primary and secondary) will be carried out for all randomized patients (ITT) including Class III/IV+/- V and pure Class V LN (N= up to 279).

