Objective	Same as Primary	Same as primary	Same as primary	Same as primary
Estimand Label	Sensitivity 1 to Primary Estimand	Sensitivity 2 to Primary Estimand	Sensitivity 3 to Primary Estimand	Sensitivity 4 to Primary Estimand
Estimand/Sensitivity Analysis Description (with Endpoint)	Treatment difference (Zetomipzomib – Placebo) in proportion of patients achieving CRR at Week 37 as measured by logistic regression.	Treatment difference (Zetomipzomib – Placebo) in proportion of patients achieving CRR at Week 37 regardless of intercurrent events IE1-IE3.	Treatment difference (Zetomipzomib – Placebo) in proportion of patients achieving CRR at Week 37 in subset of population that did not require additional medication.	Treatment difference (Zetomipzomib – Placebo) in proportion of patients achieving CRR at Week 37 in subset of population who completed treatment through Week 37.
Target Population	Same as primary	Patients in the ITT Population with confirmed Class III/IV +/- V LN that had intercurrent events IE1- IE4.	Subset of patients in the ITT Population with confirmed Class III/IV +/- V LN who did not require additional medication (including rescue therapy and protocol prohibited medications) or change in background medications prior to Week 37	Subset of patients in the ITT Population with confirmed Class III/IV +/- V LN who completed treatment through Week 37
Endpoint	Same as primary	Same as primary	Same as primary	Same as primary
Estimator	Logistic regression model will include study treatment, region, baseline UPCR, and the stratification factors	Same as primary	Same as primary	Same as primary
Treatment Conditions	Same as primary	Same as primary	Same as primary	Same as primary

Objective	Same as Primary	Same as primary	Same as primary	Same as primary
Estimand Label	Sensitivity 1 to Primary Estimand	Sensitivity 2 to Primary Estimand	Sensitivity 3 to Primary Estimand	Sensitivity 4 to Primary Estimand

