Population-Level Summary	Difference in proportion of patients achieving CRR at Week 37 between patients assigned to zetomipzomib versus patients assigned to placebo, regardless of adherence in patients with confirmed Class III/IV +/- V LN, while correcting for baseline factors	Difference in proportion of patients achieving CRR at Week 37 between patients assigned to zetomipzomib versus patients assigned to placebo, regardless of adherence and regardless of having intercurrent events IE1-IE4 in patients with confirmed Class III/IV +/- V LN	Difference in proportion of patients achieving CRR at Week 37 between patients assigned to zetomipzomib versus patients assigned to placebo, regardless of adherence in patients with confirmed Class III/IV +/- V LN who did not require additional medication (including rescue therapy and protocol prohibited medications) or change in background medications prior to Week 37	Difference in proportion of patients achieving CRR at Week 37 between patients assigned to zetomipzomib versus patients assigned to placebo, regardless of adherence in patients with confirmed Class III/IV +/- V LN completed treatment through Week 37
IE1 (TF)	Composite	Treatment Policy	Principal Stratum	Composite
IE2 (Discontinue Study)	Composite	Treatment Policy	Principal Stratum	Composite
IE3 (Death)	Composite	Composite	Composite	Composite
Missing Data Handling	Same as primary	All available assessments will be used, regardless of intercurrent events (except Death). Missing data will not be imputed, instead a Tipping Point Analysis will be performed.	Same as primary	Same as primary

Objective	Same as Primary	Same as primary	Same as primary	Same as primary
Estimand Label	Sensitivity 1 to Primary Estimand	Sensitivity 2 to Primary Estimand	Sensitivity 3 to Primary Estimand	Sensitivity 4 to Primary Estimand

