8.2.3. Sensitivity Analyses

8.2.3.1. Sensitivity Analyses to the Primary Estimand

The following sensitivity analyses which are described in detail in Table 5 will be performed for the primary estimand to assess treatment difference (Zetomipzomib – Placebo) in proportion of patients achieving CRR at Week 37:

- As measured by logistic regression
- Regardless of intercurrent events IE1-IE4
- In subset of population that did not require additional medication or change in background medication
- In subset of population who completed treatment through Week 37

The first sensitivity analysis of the primary estimand will be conducted in the ITT Population (Class III/IV +/- V patients only) will be estimated from the logistic regression model using the methodology described in Ge et al (Ge et al., 2011). The model will include covariates for treatment, stratification factors (LN Class, IV methylprednisolone), baseline 24-hour UPCR value (as a continuous number, not a stratification factor), and geographic region.

The secondary estimand is similar to the primary estimand, but estimates the difference in proportion of patients achieving CRR at Week 37 between patients assigned to zetomipzomib versus patients assigned to placebo, regardless of adherence in patients with confirmed Class III/IV +/- V or pure Class V LN.

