8.2.3.3. Sensitivity Analysis using Tipping Point

For the tipping point analyses, let M1 and M2 be the total number of patients with missing CRR assessment at Week 37 in the zetomipzomib and pooled placebo groups, respectively. There are overall (M1+1)*(M2+1) possible ways for imputing missing data as responders or non-responders in this analysis, ranging from imputing all missing values as non-responders to imputing all missing values as responders in each of the two treatment groups. For each of the (M1+1)*(M2+1) different imputation patterns, the same statistical method as the primary analysis will be used for testing statistical significance and the output will be plotted in a rectangle for inspection. The staircase region that separates significant and non-significant outcomes forms the tipping-point boundary.

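### Sensitivity 2, the SAP's only treatment-policy analysis of Week 37 CRR, is defined on patients who had an intercurrent event rather than on all Class III/IV +/- V ITT patients

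*SAP*

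**What the plan says.** SAP Table 5 lists seven analyses of CRR at Week 37: three estimands and four sensitivity analyses. Its Target Population row fixes who is analysed in each. For Sensitivity 2 the entry is "Patients in the ITT Population with confirmed Class III/IV +/- V LN that had intercurrent events IE1- IE4".

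Other cells in the same column say something different:

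- The description asks for the treatment difference "in proportion of patients achieving CRR at Week 37 regardless of intercurrent events IE1-IE3".
- The population-level summary is "regardless of adherence and regardless of having intercurrent events IE1-IE4 in patients with confirmed Class III/IV +/- V LN".
- IE1 (treatment failure) and IE2 (study discontinuation) are assigned treatment policy; IE3 (death) is composite.
- On missing data: "All available assessments will be used, regardless of intercurrent events (except Death"), followed by a tipping-point analysis in place of imputation.

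SAP Section 8.2.3.1 lists the analysis as "Regardless of intercurrent events IE1-IE4". SAP Table 4 defines IE1, IE2 and IE3 only.

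Protocol Table 6 gives the treatment-policy rule that Sensitivity 2 implements: "For patients who had an IE and remained in the study, the observed efficacy data at Week 37 will be included in the analysis". Protocol Section 10.6.1.1 adds: "The primary analysis of the primary estimand and secondary estimand(s) will be carried out for randomized patients (ITT) with Class III/IV+/- V LN (N=249"). SAP Section 13 reports that the intercurrent events were redefined and relabelled, but declares no restriction of this analysis to patients who had one.

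**The concern.** A treatment-policy analysis compares everyone as randomized and counts the observed outcome whether or not an event occurred. Restricting it to patients with an event selects on a post-randomization variable that treatment may influence. The arms are then no longer protected by randomization, and the result cannot be an effect regardless of events.

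The literal reading could even be degenerate. The endpoint cell for Sensitivity 2 is the same as for the primary estimand, and SAP Section 8.2 requires a responder to complete Week 37 and not be a treatment failure. If that rule carries over, nobody in the restricted set with an event before Week 37 could respond, and the comparison would be 0% against 0%.

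Sensitivity 2 is the only column of Table 5 that uses treatment policy. Sensitivity 3 also leaves the composite rule, but through a principal stratum. The role matters more in the SAP than in the protocol. Footnote b of protocol Table 6 kept observed data in the primary estimand for patients who stopped study drug without rescue or prohibited medication and stayed in the study. SAP Table 4 and Section 8.2.2 make every study-drug discontinuation before Week 37 a non-response. Sensitivity 2 is where those observed outcomes should count.

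**Working it through.** **1. The design figure for the full set.** Inputs from SAP Section 4.2: 83 per group, 40% versus 20%, two-sided 0.05, pooled variance.

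Power = Φ{[0.20·√83 − 1.96·√(2·0.30·0.70)] / √(0.40·0.60 + 0.20·0.80)} = Φ{(1.822 − 1.270)/0.632} = Φ(0.873) = 80.9%.

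The plan states 80%, and 82 per group would suffice, so the figure reproduces. It belongs to all 249 patients and does not describe a subset.

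**2. Which population does each statement imply?**

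| Place | Implied population |
|---|---|
| SAP Table 5, Sensitivity 2, Target Population | Only patients with an event |
| Same column, description | All, whatever the event status |
| Same column, population-level summary | All Class III/IV +/- V as assigned |
| Same column, strategy for IE1 and IE2 | All (treatment policy) |
| Same column, missing data | All available assessments |
| Same column, rationale | Says patients with events are included; fits either reading |
| SAP 8.2.3.1 | No restriction; the next two bullets do name a subset |
| Protocol Table 6, treatment policy | Patients with an event contribute within the overall analysis |

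One cell stands alone. Two label faults add to it. IE4 appears in the Target Population cell, the population-level summary and Section 8.2.3.1, but no IE4 exists. The description covers IE3 (death), while the IE3 row and the missing-data cell treat death as composite.

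**3. How many patients the cell would keep.** The documents give no event rate, so the shares are assumed.

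| Assumed share with an event | Kept of 249 | Left out | Kept of 166 (one dose versus pooled placebo) |
|---|---|---|---|
| 10% | 24.9, about 25 | 224 | 16.6, about 17 |
| 25% | 62.25, about 62 | 187 | 41.5, about 42 |
| 40% | 99.6, about 100 | 149 | 66.4, about 66 |

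**4. How far the estimate could move.** Assume a 25% event share in both arms and full-set response of 40% versus 20%. Full-set rate = 0.75 × event-free rate + 0.25 × post-event rate, solved for the event-free rate.

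| Post-event response, active/placebo | Event-free response needed | Full-set difference | Difference from the cell as written |
|---|---|---|---|
| 0% / 0% | 53.3% / 26.7% | 20 points | 0 points |
| 10% / 5% | 50.0% / 25.0% | 20 points | 5 points |
| 20% / 10% | 46.7% / 23.3% | 20 points | 10 points |

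For the second row: 0.75 × 50 + 0.25 × 10 = 40 and 0.75 × 25 + 0.25 × 5 = 20.

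**The case against.** The strongest reply is that the document resolves its own slip. Where Table 5 means a subset, as for Sensitivities 3 and 4, it says so in words; Sensitivity 2 does not. The rationale cell speaks of including patients with events as an inherent part of treatment, which suits a wider set better. Harm requires programming one cell against the rest of its column, in a supportive analysis outside the multiplicity scheme. This supports calling it a drafting error. It does not make the cell safe, because that row defines the analysed set and its clause is restrictive.

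The protocol's N=249 sentence is also weaker support than it looks. The secondary-estimand column of protocol Table 6 itself contains a per-protocol set and two principal strata, so the sentence may only name the source population. That is fair; the treatment-policy line in the same table is the better evidence.

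Protocol Section 10.6.4 also plans analyses on all observed data. It lists these among missing-data methods and does not set a strategy for intercurrent events.

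Finally, the 20-point full-set difference is built in, and the 40% and 20% design rates belong to an endpoint on which treatment failures cannot respond. Holding them as composite rates fixes event-free response at 53.3% and 26.7%. The treatment-policy difference is then 20 + 0.25 × 5 = 21.25 points for post-event response of 10/5 percent, and 20 + 0.25 × 10 = 22.5 points for 20/10 percent. The criticism is right about the illustration, but the gap from the event-only result (5 or 10 points) becomes slightly larger.

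**Conclusion.** The concern holds. As written, the Target Population of Sensitivity 2 contradicts the rest of its column, SAP Section 8.2.3.1 and the protocol's treatment-policy rule, and SAP Section 13 does not declare the change. Followed literally, it would compare arms within a group formed after randomization and could not deliver the stated effect.

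The size cannot be fixed from the documents, because they give neither an event rate nor a post-event response rate; the counts and point differences above are illustrations under stated assumptions. The damage is confined to one supportive analysis: the primary analysis, type I error control and interim rules stand. It should still be corrected, because choosing the population after unblinding would forfeit prespecification of the SAP's only treatment-policy result.

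**What to change.** Before unblinding, amend the SAP as follows:

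1. Set the Sensitivity 2 Target Population to *Same as primary*: all ITT patients with Class III/IV +/- V LN, with or without an event.
2. State that observed Week 37 CRR counts after IE1, so the Section 8.2 bar on treatment failures does not apply to this analysis, and that death (IE3) remains non-response.
3. Change the description to cover IE1 and IE2 only. Replace the three references to IE1-IE4 (Target Population cell, population-level summary, Section 8.2.3.1) to match.
4. State that patients who leave the study with no assessment in the Week 37 window (Days 240 to 281 for 24-hour urine, SAP Table 3) count as missing and enter the tipping-point analysis of Section 8.2.3.3, where "There are overall (M1+1)*(M2+1) possible ways for imputing missing data as responders or non-responders in this analysis". Multiple imputation within Sensitivity 2 is optional, since Section 8.2.3.2 already plans it separately.

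The cost is wording: one cell, one description line, three labels and two clarifying statements. No new data or methods are needed.

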8.2.2. Primary Analysis

The primary analysis of the primary estimand will be conducted when all Class III/IV+/- V LN patients in the ITT Population reach (or would have reached) Week 37. Patients who experience an intercurrent event (IE) as specified in Table 4 above prior to the Week 37 visit will be considered non-responders (ie, will be imputed as not achieving CRR) by using the composite IE strategy. Patients with missing CRR assessment at Week 37 due to any other reason will also be considered non-responders through imputation in the missing data strategy.

The proportion of patients achieving CRR at Week 37 will be compared between zetomipzomib and placebo (separately for each of the two dose groups and the combined dose groups vs. pooled placebo) using the CMH test at 2-sided 5% level of significance, stratified by the randomization stratification factors specified in Section 3.5. The following statistics will be presented:

- Number and proportion of patients achieving CRR
- Weighted difference in CRR proportions
- Odds ratio and associated 2-sided 95% CI
- p-value for each pairwise comparison between zetomipzomib and placebo

A bar graph showing the proportion of patients achieving CRR by treatment group with the weighted treatment difference and CMH p-value will be produced.

The CMH assumption of homogeneous treatment effect across strata will be tested using the Breslow-Day test. A significant Breslow-Day test (p-value <0.05) indicates that the treatment effect is not homogeneous across strata. Unstratified chi-square methods may also be used to analyze the primary estimand.

8.2.3. Sensitivity Analyses

8.2.3.1. Sensitivity Analyses to the Primary Estimand

The following sensitivity analyses which are described in detail in Table 5 will be performed for the primary estimand to assess treatment difference (Zetomipzomib – Placebo) in proportion of patients achieving CRR at Week 37:

- As measured by logistic regression
- Regardless of intercurrent events IE1-IE4
- In subset of population that did not require additional medication or change in background medication
- In subset of population who completed treatment through Week 37

The first sensitivity analysis of the primary estimand will be conducted in the ITT Population (Class III/IV +/- V patients only) will be estimated from the logistic regression model using the methodology described in Ge et al (Ge et al., 2011). The model will include covariates for treatment, stratification factors (LN Class, IV methylprednisolone), baseline 24-hour UPCR value (as a continuous number, not a stratification factor), and geographic region.

The secondary estimand is similar to the primary estimand, but estimates the difference in proportion of patients achieving CRR at Week 37 between patients assigned to zetomipzomib versus patients assigned to placebo, regardless of adherence in patients with confirmed Class III/IV +/- V or pure Class V LN.

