Sensitivity analyses of the primary endpoint will be performed using other missing data handling approaches, specifically MI and tipping point analysis.

Supplemental analyses on the primary and selected key secondary endpoints may be performed using logistic regression models. These analyses will include covariates for treatment, UPCR at baseline (stratification factor), biopsy class, IV methylprednisolone use at Baseline (stratification factor), and region and other selected baseline parameters.

Details on which of these analyses will include patients with Class III/IV+/- V LN, or patients with Class III/IV+/- V and pure Class V LN will be provided in the SAP.

As indicated in Section 9.10, a CEC will adjudicate CRR (primary efficacy endpoint) by reviewing blinded data for patients in this study. All adjudication decisions of the CEC will be appropriately documented. The adjudication covers cases of treatment failure as well.

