3.5. Randomization, Stratification, and Blinding

Patients who have provided informed consent (IC) and passed study inclusion/exclusion criteria per Sections 4.2 and 4.3 of the study protocol will be randomized via the system.

Patients will be randomized to receive either zetomipzomib (30 mg or 60 mg) or matching placebo in a 2:1:2:1 ratio (zetomipzomib 30 mg: 30 mg matching placebo: zetomipzomib 60 mg: 60 mg matching placebo). Randomization will occur at Day 1 (Week 1) prior to the first dose of zetomipzomib or placebo and will be stratified by:

- LN Class (Class III/IV +/- V and pure Class V)
- Average 24-hour UPCR at the Screening visit (\leq 3.0 and \geq 3.0)
- IV methylprednisolone planned total dose (0 to <500 mg, 500-1000 mg, or >1000 to 3000 mg) Note: no more than 20% of the patients may be stratified into the >1000 to 3000 mg group.

All study personnel and patients may know if the patient is in the low dose group (30 mg or matching placebo) or the high dose group (60 mg or matching placebo). Randomized treatment assignment within dose group (ie, to zetomipzomib or matching placebo) at the patient level will remain blinded to all patients and all Sponsor, contract research organization (CRO;), and site personnel involved in the day-to-day conduct of the study until the proper unblinding procedures have been followed. To preserve the blind with respect to active treatment and placebo, patients randomized to the placebo group will receive a subcutaneous injection in an equivalent volume to the active zetomipzomib injection and on the same dosing schedule.

Additional details regarding planned unblinding during the course of the study are documented in a separate Blinding Management Plan. Details regarding emergency unblinding of a patient due to safety concerns are documented in Section 3.2.3 of the study protocol and the User Manual. Any patients unblinded for safety reasons will be clearly identified in the data listings.

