6.2. Baseline Disease Characteristics

The following baseline disease characteristics from the "Medical History – Systemic Lupus Erythematosus" eCRF page will be summarized by treatment group and overall for the ITT Population and the Safety Population.

- Time from SLE diagnosis to Screening (years)
 - Calculated as [(Screening date SLE diagnosis date)/365.25]
 - Partial SLE diagnosis date will be imputed as specified in Section 4
- Time from LN diagnosis to Screening (years)
 - Calculated as [(Screening date LN diagnosis date)/365.25]
 - Partial LN diagnosis date will be imputed as specified in Section 4
- Time from renal biopsy used for study inclusion to Screening (months)
 - If biopsy performed prior to Screening visit, calculate as [(Screening date renal biopsy date)/30.44]
 - If biopsy performed during Screening period, set to 0

- Did patient have protocol-required chest x-ray (Yes, No)
 - If Yes:
 - When was chest x-ray performed (During Screening period, Within 90 days of IC)
 - Results (Normal; Abnormal, not clinically significant [NCS]; Abnormal, clinically significant [CS])
 - Did chest x-ray show evidence suggestive of active tuberculosis (TB) disease (Yes, No)
- LN class as integrated from RTSM (Class III/IV +/- V LN, pure Class V LN) stratification factor
- LN classes: Class III only, Class IV only, Class III + V, Class IV + V, Class V only
- Lesions (Class III/IV)
 - Chronic only {should be screen failure; do not present category on table if n=0}
 - Active only
 - Active and chronic
 - Unknown
- Average 24-hour UPCR as integrated from RTSM ($\leq 3.0, >3.0$) stratification factor
- 24-hour UPCR (mg/mg)
 - See Section 4 for derivation of baseline 24-hour UPCR
- eGFR value (mL/min/1.73 m^2) (<60, \geq 60)
- Treatment naïve (none or ≤3 months) (Yes, No)
- Number of prior LN flares (excluding the current flare)
- Treatment refractory (Yes, No, Not Available)
 - If Yes, summarize the number and percentage of patients with each applicable prior treatment
 - Cyclophosphamide
 - Mycophenolate/MMF
 - Tacrolimus
 - Voclosporin
 - Cyclosporin
 - Rituximab
 - Obinutuzumab
 - Belimumab
 - Anifrolumab
 - Leflunomide

- Bortezomib
- Eculizumab
- IV immunoglobulin
- Other
- IV methylprednisolone planned total dose as integrated from RTSM (0 to <500 mg, 500-1000 mg, or >1000 to 3000 mg) stratification factor

The following additional baseline information will be similarly summarized for the ITT Population:

- Anti-dsDNA antibody (IU/mL)

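### In the covariate-adjusted sensitivity analysis LN Class has only one level, so the model contains no histology term; the collected biopsy class should take its place

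*SAP*

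**What the plan says.** SAP 8.2.3.1 fixes the population: "The first sensitivity analysis of the primary estimand will be conducted in the ITT Population (Class III/IV +/- V patients only"). It then lists the covariates: "The model will include covariates for treatment, stratification factors (LN Class, IV methylprednisolone), baseline 24-hour UPCR value", with UPCR entered on its continuous scale in place of the randomization stratum, plus geographic region. SAP 3.5 defines the first of those factors by two levels: "LN Class (Class III/IV +/- V and pure Class V").

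Protocol 10.6.1.1 introduced the analysis as optional: "Supplemental analyses on the primary and selected key secondary endpoints may be performed using logistic regression models". Its covariate list reads: "These analyses will include covariates for treatment, UPCR at baseline (stratification factor), biopsy class, IV methylprednisolone use at Baseline (stratification factor), and region", plus other baseline parameters to be selected. UPCR and IV methylprednisolone carry the stratification-factor label there; biopsy class does not. The protocol leaves it to the SAP to say which of these analyses include pure Class V patients.

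SAP Section 13 prints both covariate sentences but describes only one difference, the change from the UPCR stratum to the continuous value. SAP Table 5 gives the same model more briefly, as treatment, region, baseline UPCR and the stratification factors. SAP 8.3 carries the method to the five key secondary endpoints.

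A finer histology variable is available. SAP 6.2 tabulates "LN classes: Class III only, Class IV only, Class III + V, Class IV + V, Class V only", and SAP 8.2.4 uses the same classes as a subgroup.

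**The concern.** Table 5 gives the purpose of sensitivity analysis 1 as control of baseline covariates. One of the covariates listed for it cannot vary once the population is limited to Class III/IV +/-V. A reader who sees LN Class in the model would reasonably think histology has been adjusted for, and it has not.

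The protocol's list contained a covariate that could have done this, and Protocol 10.1 commits the SAP to explaining substantive changes to the planned analysis. Section 13 does not say why LN Class now stands where biopsy class stood. At stake are some precision and protection against chance imbalance in histology, in one sensitivity analysis and its key secondary counterparts. If the wording stays, whoever programs the model must decide what to do with the empty term, possibly after unblinding.

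**Working it through.** **Plan's own figure.** SAP 4.2 states 80% power for 40% versus 20% with 83 per group, two-sided 0.05, pooled variance.

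- Sample size: n = [1.96 x sqrt(2 x 0.30 x 0.70) + 0.8416 x sqrt(0.20 x 0.80 + 0.40 x 0.60)]^2 / 0.20^2 = (1.270 + 0.532)^2 / 0.04, which rounds up to 82 per group.
- Power at 83 per group is 80.9%.

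The stated figure reproduces, and nothing below changes it.

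**Rank of the model.** One pairwise comparison has 2 x 83 = 166 patients. Indicator columns were built for the listed covariates, with simulated values.

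| Model | Columns | Rank |
|---|---|---|
| As written: intercept 1, treatment 1, LN Class 1, methylprednisolone 2, region 3, UPCR 1 | 9 | 8 |
| LN Class removed | 8 | 8 |
| LN Class replaced by four-level biopsy class (III, III+V, IV, IV+V) | 11 | 11 |

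LN Class duplicates the intercept and adds 0 degrees of freedom. Fitted values and the treatment estimate are the same with or without it. Four-level biopsy class would add 3 estimable terms, and with versus without Class V would add 1.

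**Primary CMH test.** The three stratification factors give 2 x 2 x 3 = 12 nominal strata. Within Class III/IV +/-V, LN Class has one level, so 1 x 2 x 3 = 6 strata remain. The others are empty and do not affect the test.

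**Room for extra terms.** At the planning rates the average response is (0.20 + 0.40) / 2 = 0.30, which gives 0.30 x 166 = 49.8, about 50 responders.

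- Now: 7 estimable non-intercept terms (1 + 2 + 3 + 1), 49.8 / 7 = 7.1 responders per term.
- With versus without Class V: 8 terms, 49.8 / 8 = 6.2.
- Four-level biopsy class: 10 terms, 49.8 / 10 = 5.0.

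**Possible gain.** The documents give neither the class mix nor CRR by class, so these inputs are assumptions.

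- Suppose 30% have a Class V component, with CRR 15% against 25% in the rest. The mean is 0.7 x 0.25 + 0.3 x 0.15 = 0.22 and the total variance 0.22 x 0.78 = 0.1716. The between-class variance is 0.7 x 0.3 x 0.10^2 = 0.0021, a share of 1.2%.
- With a 20-point gap at the same mean (28% and 8%), the between-class variance is 0.7 x 0.3 x 0.20^2 = 0.0084, a share of 4.9%.
- As patients per group: 83 x 0.012 = 1.0 and 83 x 0.049 = 4.1.
- Alternatively, take four equal classes with a standard deviation of CRR across classes of 5 or 10 points in both arms. The variance of the risk difference falls by 2 x 0.05^2 / (0.16 + 0.24) = 1.25%, or 2 x 0.10^2 / 0.40 = 5%.

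These are marginal gains. The model already contains continuous baseline UPCR, so any association between class and proteinuria makes the added gain smaller.

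**The case against.** The strongest reply is that this is a matter of tidying. An empty term leaves the treatment estimate unchanged, the protocol made the analysis optional, histology is already examined as a subgroup in SAP 8.2.4, and the choice of covariates for a sensitivity model is partly preference. All of that stands and keeps the point minor. It does not answer the finding that the model lists a histology covariate and contains none.

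Some stronger readings that a reader might infer are not supported:

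- *The SAP dropped a four-level histology covariate without disclosing it.* Protocol 10.6.1.1 gives no levels for biopsy class. Its trio of UPCR, biopsy class and IV methylprednisolone resembles the three stratification factors, so the LN Class stratum may have been meant. Against that, biopsy class lacks the stratification-factor label, and Protocol 10.8.2 lists LN Class and pathology class separately. The meaning is unsettled. Section 13 also prints both lists, so the difference is visible though unexplained. On either reading the SAP model has no histology term.
- *Table 5 enters UPCR twice.* Read alone it could. SAP 8.2.3.1 and Section 13 settle that UPCR enters once, as a continuous value; Table 5 needs only matching wording.
- *The main histological difference is ignored.* The documents do not say that CRR differs among III, IV, III+V and IV+V. Protocol 1.1.2 groups III and IV as the more aggressive forms and describes only pure Class V as more resistant; those patients are not in this model.
- *Adding biopsy class is free.* It takes one to three terms in a model with about 50 responders.

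**Conclusion.** The point holds as a minor defect of specification. In sensitivity analysis 1 LN Class is constant, so the covariate-adjusted model makes no adjustment for histology. This follows from the population in SAP 8.2.3.1 and the factor definition in SAP 3.5, and needs no assumption.

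There is no bias in the treatment estimate, no effect on the primary CMH test and no change to sample size or power. What is lost is a small possible gain in precision, about 1% to 5% of variance or the equivalent of roughly 1 to 4 patients per group of 83. That range rests on assumed class shares and response gaps, and overlap with baseline UPCR would lower it. The firmer reason to act is that the model would then match its stated purpose and leave no choice open at programming.

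**What to change.** - In SAP 8.2.3.1, and in the key secondary version in 8.3, replace LN Class with the biopsy pathology class already collected. Prefer with versus without a Class V component (1 degree of freedom), because about 50 responders per pairwise comparison limit a four-level term. If four levels are wanted, pre-specify a rule for merging sparse classes.
- Keep LN Class only in models that include pure Class V patients.
- Reword the Table 5 entry to match 8.2.3.1, with continuous baseline UPCR entered once.
- In Section 13, state that LN Class stood in place of the protocol's biopsy class, say what biopsy class is taken to mean, and record the replacement.

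The cost is a SAP wording change before unblinding and one to three extra model terms. No new data are needed.
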